12.8. Appendix 8: Values of Potential Clinical Importance

12.8.1. Laboratory Values

Haematology				
Laboratory Parameter	Units	Category	Clinical Concern Range	
			Low Flag (< x)	High Flag (>x)
Hematocrit	Ratio of 1	Male		0.54
		Female		0.54
		Δ from BL	↓0.075	
Hemoglobin	g/L	Male		180
		Female		180
		Δ from BL	↓25	
Lymphocytes	x10 ⁹ /L		0.8	
Neutrophil Count	x10 ⁹ /L		1.5	
Platelet Count	x10 ⁹ /L		100	550
While Blood Cell Count (WBC)	x10 ⁹ /L		3	20
Clinical Chemistry				
Laboratory Parameter	Units	Category	Clinical Concern Range	
			Low Flag (< x)	High Flag (>x)
Albumin	g/L		30	
Calcium	mmol/L		2	2.75
Creatinine	μmol/L	Δ from BL		↑ 44.2
Glucose	mmol/L		3	9
Magnesium	mmol/L		0.5	1.23
Phosphorus	mmol/L		0.8	1.6
Potassium	mmol/L		3	5.5
Sodium	mmol/L		130	150
Total CO2	mmol/L		18	32
Liver Function				
Test Analyte	Units	Category	Clinical Concern Range	
ALT/SGPT	U/L	High	≥ 2x ULN	
AST/SGOT	U/L	High	≥ 2x ULN	
AlkPhos	U/L	High	≥ 2x ULN	
T Bilirubin	μmol/L	High	≥ 1.5xULN	
T. Bilirubin + ALT	μmol/L U/L	High	1.5xULN T. Bilirubin + ≥ 2x ULN ALT	

12.8.2. ECG

ECG Parameter	Units	Clinical Concern Range	
		Lower	Upper
Absolute			
Absolute QTc Interval	msec	> 450	≤ 479
		≥ 480	≤ 499
		≥ 500	
Absolute PR Interval	msec	< 110	> 220
Absolute QRS Interval	msec	< 75	> 110
Change from Baseline			
Increase from Baseline QTc	msec	> 30	<60
	msec	≥ 60	

12.8.3. Vital Signs

Vital Sign Parameter (Absolute)	Units	Clinical Concern Range	
		Lower	Upper
Systolic Blood Pressure	mmHg	< 85	> 160
Diastolic Blood Pressure	mmHg	< 45	> 100
Heart Rate	bpm	< 40	> 110

Vital Sign Parameter (Change from Baseline)	Units	Clinical Concern Range			
		Decrease		Increase	
		Lower	Upper	Lower	Upper
Systolic Blood Pressure	mmHg	≥ 20	≥ 40	≥ 20	≥ 40
Diastolic Blood Pressure	mmHg	≥ 10	≥ 20	≥ 10	≥ 20
Heart Rate	bpm	≥ 15	≥ 30	≥ 15	≥ 30

12.9. Appendix 9: Abbreviations & Trade Marks

12.9.1. Abbreviations

Abbreviation	Description
AE	Adverse Event
A&R	Analysis and Reporting
AIC	Akaike's Information Criteria
BID	Twice a day
CI	Confidence Interval
CRF	Case Report Form
CRP	C-Reactive Protein
CSR	Clinical Study Report
C-SSRS	Columbia Suicide Severity Rating Scale
CTR	Clinical Trial Register
CV _b / CV _w	Coefficient of Variation (Between) / Coefficient of Variation (Within)
DB	Double-Blind
DBF	Database Freeze
DBR	Database Release
DOB	Date of Birth
DP	Decimal Places
DRC	Data Review Committee
ECG	Electrocardiogram
eCRF	Electronic Case Record Form
EMA	European Medicines Agency
FCP	Faecal Calprotectin
FDA	Food and Drug Administration
FDAAA	Food and Drug Administration Clinical Results Disclosure Requirements
GEE	Generalised Estimating Equations
GSK	GlaxoSmithKline
IA	Interim Analysis
IBDQ	Inflammatory Bowel Disease Questionnaire
ICH	International Conference on Harmonization
IDSL	Integrated Data Standards Library
IMMS	International Modules Management System
IP	Investigational Product
IRTS	Interactive Response Technology System
ITT	Intent-To-Treat
Kg	Kilogram
mmol	Millimole
MMRM	Mixed Model Repeated Measures
MRS	Modified Riley Scale
NR	Normal Range
OL	Open-Label
PCI	Potential Clinical Importance
PD	Pharmacodynamic
PDMP	Protocol Deviation Management Plan
PK	Pharmacokinetic
PopPK	Population PK
PP	Per Protocol

Abbreviation	Description
PP	Per Protocol
PSRAE	Possible Suicidality-Related Adverse Event
PT	Preferred Term
QC	Quality Control
QTcB	Bazett's QT Interval Corrected for Heart Rate
QTcF	Frederica's QT Interval Corrected for Heart Rate
RAMOS	Randomization & Medication Ordering System
RAP	Reporting & Analysis Plan
RHI	Robarts Histology Index
SAC	Statistical Analysis Complete
SAE	Serious Adverse Event
SE	Standard Error
SOC	System Organ Class
SOP	Standard Operation Procedure
SRT	Safety Review Team
TA	Therapeutic Area
TEAR1	Target Engagement Assay RIP1
TFL	Tables, Figures & Listings
TID	Three times a day
UC	Ulcerative Colitis
UCEIS	Ulcerative Colitis Endoscopic Index of Severity
ULN	Upper Limit of Normal

12.9.2. Trademarks

Trademarks of the GlaxoSmithKline Group of Companies
RandALL

Trademarks not owned by the GlaxoSmithKline Group of Companies
MedDRA
NONMEM
SAS

12.10. Appendix 10: List of Data Displays

12.10.1. Data Display Numbering

The following numbering will be applied for RAP generated displays:

Section	Tables	Figures
Study Population	1.1 to 1.16	NA
Efficacy	2.1 to 2.41	2.1 to 2.44
Safety	3.1 to 3.56	3.1 to 3.7
Pharmacokinetic	4.1	4.1 to 4.28
Pharmacodynamic and / or Biomarker	6.1 to 6.11	6.1 to 6.19
Section	Listings	
ICH Listings	1 to 42	
Other Listings	43 to 83	

12.10.2. Mock Example Shell Referencing

Non IDSL specifications will be referenced as indicated and if required example mock-up displays provided in [Appendix 11](#): Example Mock Shells for Data Displays

Section	Figure	Table	Listing
Study Population	POP_Fn	POP_Tn	POP_Ln
Efficacy	EFF_Fn	EFF_Tn	EFF_Ln
Safety	SAFE_Fn	SAFE_Tn	SAFE_Ln
Pharmacokinetic	PK_Fn	PK_Tn	PK_Ln
Pharmacodynamic and / or Biomarker	PD_Fn	PD_Tn	PD_Ln

NOTES:

- Non-Standard displays are indicated in the 'IDSL / Example Shell' or 'Programming Notes' column as '[Non-Standard] + Reference.'

12.10.3. Deliverables

Delivery [Priority] ^[1]	Description
IA SAC [X]	Interim Analysis Statistical Analysis Complete
SAC [X]	Final Statistical Analysis Complete
SAC2 [X]	Post-Final Statistical Analysis Complete

NOTES:

- Indicates priority (i.e. order) in which displays will be generated for the reporting effort

12.10.4. Study Population Tables

Study Population Tables					
No.	Population	IDSL / Example Shell	Title	Programming Notes	Deliverable [Priority]
Subject Disposition					
1.1.	Safety	ES1	Summary of Subject Disposition for the Subject Conclusion Record by Randomised Treatment	ICH E3, FDAAA, EudraCT Footnote: Add footnote : Note: "Subjects" is used to refer to "Participants" in all data displays to reflect GSK Display Standards	IA SAC[1], SAC [1]
1.2.	Safety	SD1	Summary of Treatment Status and Reasons for Discontinuation of Study Treatment by Randomised Treatment	ICH E3	IA SAC [1], SAC [1]
1.3.	All Subjects	ES6	Summary of Screening Status and Reasons for Screen Failure by Randomised Treatment	Journal Requirements	IA SAC [1], SAC [1]
1.4.	All Subjects	NS1	Summary of Number of Subjects by Country and Site ID by Randomised Treatment	EudraCT/Clinical Operations	IA SAC [1], SAC [1]
Protocol Deviation					
1.5.	Safety	DV1	Summary of Important Protocol Deviations by Randomised Treatment	ICH E3	IA SAC [1], SAC [1]
Population Analysed					
1.6.	Safety	SP1	Summary of Study Populations by Randomised Treatment	IDSL	IA SAC [1], SAC [1]
1.7.	Safety	SP2 / SP2A	Summary of Exclusions from the PP and PP + Completers Population	IDSL	IA SAC [1], SAC [1]

Study Population Tables					
No.	Population	IDSL / Example Shell	Title	Programming Notes	Deliverable [Priority]
Demographic and Baseline Characteristics					
1.8.	Safety	DM1	Summary of Demographic Characteristics by Randomised Treatment	ICH E3, FDAAA, EudraCT If height and weight are collected only at baseline, then display in this demographic summary. Otherwise display height and weight with the vital signs data.	IA SAC [1], SAC [1]
1.9.	All Subjects	DM11	Summary of Age Ranges by Randomised Treatment	EudraCT	IA SAC [1], SAC [1]
1.10.	Safety	DM5	Summary of Race and Racial Combinations by Randomised Treatment	ICH E3, FDA, FDAAA, EudraCT	IA SAC [1], SAC [1]

Study Population Tables					
No.	Population	IDSL / Example Shell	Title	Programming Notes	Deliverable [Priority]
1.11.	Safety	DM1	Summary of Ulcerative Colitis Baseline Characteristics by Randomised Treatment	
To include: Baseline Mucosal Appearance at Endoscopy Mayo Subscore, Baseline Total Mayo Score, Baseline Partial Mayo Score Baseline 3-domain Mayo Score, Baseline UCEIS Total Score, Baseline Modified Riley Scale Score, Baseline FCP, Baseline FCP category, Baseline Concomitant Medications for UC (Glucocorticoids only, Immunosuppressants only, Glucocorticoids and Immunosuppressants, No Glucocorticoids or Immunosuppressants, Baseline Prednisone dose, Family History of Premature Coronary Artery Disease and History of Tobacco Use.
 
Include the footnote: Note: Glucocorticoids and Immunosuppressants were identified by review of all ingredients by clinical and medical team.
	IA SAC[1], SAC [1]
Prior/Current Medical Conditions and Concomitant Medications					
1.12.	Safety	MH4	Summary of Current/Past Medical Conditions by Randomised Treatment	
ICH E3 Separate summaries for Current & Past conditions, if collected.
	IA SAC [1], SAC [1]

Study Population Tables					
No.	Population	IDSL / Example Shell	Title	Programming Notes	Deliverable [Priority]
1.13.	Safety	MH1	Summary of Current/Past Cardiovascular Risk Factors by Randomised Treatment	ICH E3 Separate summaries for Current & Past, if collected	IA SAC [1], SAC [1]
1.14.	Safety	CM1	Summary of Prior Medications by Randomised Treatment	ICH E3	IA SAC [1], SAC [1]
1.15.	Safety	CM1	Summary of Concomitant Medications by Randomised Treatment	ICH E3	IA SAC [1], SAC [1]
Exposure and Treatment Compliance					
1.16.	Safety	EX1 / EX5	Summary of Exposure to Study Treatment by Randomised Treatment	ICH E3	IA SAC [1], SAC [1]

12.10.5. Safety Tables

Safety: Tables					
No.	Population	IDSL / Example Shell	Title	Programming Notes	Deliverable [Priority]
Adverse Events (AEs)					
3.1.	Safety	AE5A	Summary of All Adverse Events by Maximum Intensity by System Organ Class and Preferred Term (Part A only) by Randomised Treatment	ICH E3 Include total column across all intensities	IA SAC [1], SAC [1]
3.2.	Safety	AE5A	Summary of All Adverse Events by Maximum Intensity by System Organ Class and Preferred Term (Parts A, B and Follow-up) by Randomised Treatment	ICH E3 Include total column across all intensities	IA SAC [1], SAC [1]

Safety: Tables					
No.	Population	IDSL / Example Shell	Title	Programming Notes	Deliverable [Priority]
3.3.	Safety	AE5A	Summary of All Adverse Events by Maximum Intensity by System Organ Class and Preferred Term (Parts A, B and Follow-up) by Period Treatment	ICH E3 Include total column across all intensities	IA SAC[1], SAC [1]
3.4.	Safety	AE1	Summary of All Adverse Events by System Organ Class and Preferred Term (Part A only) by Randomised Treatment		IA SAC[1], SAC [1]
3.5.	Safety	AE1	Summary of All Adverse Events by System Organ Class and Preferred Term (Parts A, B and Follow-up) by Randomised Treatment		IA SAC[1], SAC [1]
3.6.	Safety	AE1	Summary of All Adverse Events by System Organ Class and Preferred Term (Parts A, B and Follow-up) by Period Treatment		IA SAC[1], SAC [1]
3.7.	Safety	AE3	Summary of Common ($\geq 10\%$) Adverse Events by Overall Frequency (Part A only) by Randomised Treatment	ICH E3 Common defined as $\geq 10\%$ within either randomised treatment group	IA SAC [1], SAC [1]
3.8.	Safety	AE3	Summary of Common ($\geq 10\%$) Adverse Events by Overall Frequency (Parts A, B and Follow-up) by Randomised Treatment	ICH E3 Common defined as $\geq 10\%$ within either randomised treatment group	IA SAC[1], SAC [1]
3.9.	Safety	AE3	Summary of Common ($\geq 10\%$) Adverse Events by Overall Frequency (Parts A, B and Follow-up) by Period Treatment	ICH E3 Common defined as $\geq 10\%$ within either randomised treatment group	IA SAC[1], SAC [1]
3.10.	Safety	AE5A	Summary of All Drug-Related Adverse Events by Maximum Intensity and System Organ Class and Preferred Term (Part A only) by Randomised Treatment	ICH E3 Include total column across all intensities	IA SAC [1], SAC [1]
3.11.	Safety	AE5A	Summary of All Drug-Related Adverse Events by Maximum Intensity and System Organ Class and Preferred Term (Parts A, B and Follow-up) by Randomised Treatment	ICH E3 Include total column across all intensities	IA SAC [1], SAC [1]

Safety: Tables					
No.	Population	IDSL / Example Shell	Title	Programming Notes	Deliverable [Priority]
3.12.	Safety	AE5A	Summary of All Drug-Related Adverse Events by Maximum Intensity and System Organ Class and Preferred Term (Parts A, B and Follow-up) by Period Treatment	ICH E3 Include total column across all intensities	IA SAC [1], SAC [1]
3.13.	Safety	AE15	Summary of Common ($\geq 10\%$) Non-serious Adverse Events by System Organ Class and Preferred Term (Number of Subjects and Occurrences) (Part A only) by Randomised Treatment	FDAAA, EudraCT	IA SAC [1], SAC [1]
3.14.	Safety	AE15	Summary of Common ($\geq 10\%$) Non-serious Adverse Events by System Organ Class and Preferred Term (Number of Subjects and Occurrences) (Parts A, B and Follow-up) by Randomised Treatment	FDAAA, EudraCT	IA SAC [1], SAC [1]
3.15.	Safety	AE15	Summary of Common ($\geq 10\%$) Non-serious Adverse Events by System Organ Class and Preferred Term (Number of Subjects and Occurrences) (Parts A, B and Follow-up) by Period Treatment	FDAAA, EudraCT	IA SAC [1], SAC [1]
3.16.	Safety	AE3	Summary of Common ($\geq 10\%$) Drug-Related Adverse Events by Overall Frequency (Part A only) by Randomised Treatment	ICH E3	IA SAC [1], SAC [1]
3.17.	Safety	AE3	Summary of Common ($\geq 10\%$) Drug-Related Adverse Events by Overall Frequency (Parts A, B and Follow-up) by Randomised Treatment	ICH E3	IA SAC [1], SAC [1]
3.18.	Safety	AE3	Summary of Common ($\geq 10\%$) Drug-Related Adverse Events by Overall Frequency (Parts A, B and Follow-up) by Period Treatment	ICH E3	IA SAC [1], SAC [1]
Serious and Other Significant Adverse Events					
3.19.	Safety	AE16	Summary of Serious Adverse Events by System Organ Class and Preferred Term (Number of Subjects and Occurrences) (Part A only) by Randomised Treatment	FDAAA, EudraCT	IA SAC [1], SAC [1]

Safety: Tables					
No.	Population	IDSL / Example Shell	Title	Programming Notes	Deliverable [Priority]
3.20.	Safety	AE16	Summary of Serious Adverse Events by System Organ Class and Preferred Term (Number of Subjects and Occurrences) (Parts A, B and Follow-up) by Randomised Treatment	FDAAA, EudraCT	IA SAC [1], SAC [1]
3.21.	Safety	AE16	Summary of Serious Adverse Events by System Organ Class and Preferred Term (Number of Subjects and Occurrences) (Parts A, B and Follow-up) by Period Treatment	FDAAA, EudraCT	IA SAC [1], SAC [1]
3.22.	Safety	AE1	Summary of Adverse Events Leading to Permanent Discontinuation of Study Treatment or Withdrawal from Study (Part A only) by Randomised Treatment	IDSL	IA SAC [1], SAC [1]
3.23.	Safety	AE1	Summary of Adverse Events Leading to Permanent Discontinuation of Study Treatment or Withdrawal from Study (Parts A, B and Follow-up) by Randomised Treatment	IDSL	IA SAC [1], SAC [1]
3.24.	Safety	AE1	Summary of Adverse Events Leading to Permanent Discontinuation of Study Treatment or Withdrawal from Study (Parts A, B and Follow-up) by Period Treatment	IDSL	IA SAC [1], SAC [1]
Laboratory: Chemistry					
3.25.	Safety	LB1	Summary of Chemistry Changes from Baseline (Parts A, B and Follow-up) by Randomised Treatment	ICH E3	IA SAC [1], SAC [1]
3.26.	Safety	LB1	Summary of Chemistry Changes from Period Baseline (Parts A, B and Follow-up) by Period Treatment	ICH E3	IA SAC [1], SAC [1]
3.27.	Safety	LB1	Summary of Lipids Percentage Changes from Baseline (Parts A, B and Follow-up) by Randomised Treatment	Lipids parameters = LDL Cholesterol, HDL Cholesterol, Total Cholesterol, Triglycerides and Cholesterol/HDL ratio	IA SAC [1], SAC [1]

Safety: Tables					
No.	Population	IDSL / Example Shell	Title	Programming Notes	Deliverable [Priority]
3.28.	Safety	LB1	Summary of Lipids Percentage Changes from Period Baseline (Parts A, B and Follow-up) by Period Treatment	Lipids parameters = LDL Cholesterol, HDL Cholesterol, Total Cholesterol Triglycerides and Cholesterol/HDL ratio	IA SAC[1], SAC [1]
3.29.	Safety	LB17	Summary of Worst Case Chemistry Results by PCI Criteria Post-Baseline Relative to Baseline (Parts A, B and Follow-up) by Randomised Treatment	ICH E3 (i.e. treatment emergent)	IA SAC [1], SAC [1]
3.30.	Safety	LB17	Summary of Worst Case Chemistry Results by PCI Criteria Post-Baseline Relative to Period Baseline (Parts A, B and Follow-up) by Period Treatment	ICH E3 (i.e. treatment emergent)	IA SAC [1], SAC [1]
3.31.	Safety	LB17	Summary of Worst Case Lipids Results by NR Criteria Post-Baseline Relative to Baseline (Parts A, B and Follow-up) by Randomised Treatment	Lipids parameters = LDL Cholesterol, HDL Cholesterol, Total Cholesterol Triglycerides and Cholesterol/HDL ratio	IA SAC [1], SAC [1]
3.32.	Safety	LB17	Summary of Worst Case Lipids Results by NR Criteria Post-Baseline Relative to Period Baseline (Parts A, B and Follow-up) by Period Treatment	Lipids parameters = LDL Cholesterol, HDL Cholesterol, Total Cholesterol, Triglycerides and Cholesterol/HDL ratio	IA SAC [1], SAC [1]
Laboratory: Hematology					
3.33.	Safety	LB1	Summary of Hematology Changes from Baseline (Parts A, B and Follow-up) by Randomised Treatment	ICH E3	IA SAC [1], SAC [1]
3.34.	Safety	LB1	Summary of Hematology Changes from Period Baseline (Parts A, B and Follow-up) by Period Treatment	ICH E3	IA SAC [1], SAC [1]

Safety: Tables					
No.	Population	IDSL / Example Shell	Title	Programming Notes	Deliverable [Priority]
3.35.	Safety	LB17	Summary of Worst Case Hematology Results by PCI Criteria Post-Baseline Relative to Baseline (Parts A, B and Follow-up) by Randomised Treatment	ICH E3	IA SAC [1], SAC [1]
3.36.	Safety	LB17	Summary of Worst Case Hematology Results by PCI Criteria Post-Baseline Relative to Period Baseline (Parts A, B and Follow-up) by Period Treatment	ICH E3	IA SAC [1], SAC [1]
Laboratory: Urinalysis					
3.37.	Safety	LB1	Summary of Urine Concentration Changes from Baseline (Parts A, B and Follow-up) by Randomised Treatment	ICH E3	IA SAC [1], SAC [1]
3.38.	Safety	LB1	Summary of Urine Concentration Changes from Period Baseline (Parts A, B and Follow-up) by Period Treatment	ICH E3	IA SAC [1], SAC [1]
3.39.	Safety	UR1	Summary of Worst Case Urinalysis Results (Discrete or Character Values) Post-Baseline Relative to Baseline (Parts A, B and Follow-up) by Randomised Treatment	ICH E3	IA SAC [1], SAC [1]
3.40.	Safety	UR1	Summary of Worst Case Urinalysis Results (Discrete or Character Values) Post-Baseline Relative to Period Baseline (Parts A, B and Follow-up) by Period Treatment	ICH E3	IA SAC [1], SAC [1]
Laboratory: Hepatobiliary (Liver)					
3.41.	Safety	LIVER1	Summary of Liver Monitoring/Stopping Event Reporting (Parts A, B and Follow-up) by Randomised Treatment	IDSL	IA SAC [1], SAC [1]
3.42.	Safety	LIVER1	Summary of Liver Monitoring/Stopping Event Reporting (Parts A, B and Follow-up) by Period Treatment	IDSL	IA SAC [1], SAC [1]
3.43.	Safety	LIVER10	Summary of Hepatobiliary Laboratory Abnormalities (Parts A, B and Follow-up) by Randomised Treatment	IDSL	IASAC [1], SAC [1]

Safety: Tables					
No.	Population	IDSL / Example Shell	Title	Programming Notes	Deliverable [Priority]
3.44.	Safety	LIVER10	Summary of Hepatobiliary Laboratory Abnormalities (Parts A, B and Follow-up) by Period Treatment	IDSL	IA SAC [1], SAC [1]
ECGs					
3.45.	Safety	EG1	Summary of ECG Findings (Parts A, B and Follow-up) by Randomised Treatment	IDSL	IA SAC [1], SAC [1]
3.46.	Safety	EG1	Summary of ECG Findings (Parts A, B and Follow-up) by Period Treatment	IDSL	IA SAC [1], SAC [1]
3.47.	Safety	EG10	Summary of Maximum QTc Values Post-Baseline Relative to Baseline by Category (Parts A, B and Follow-up) by Randomised Treatment	IDSL	IA SAC [1], SAC [1]
3.48.	Safety	EG10	Summary of Maximum QTc Values Post-Baseline Relative to Screening by Category (Parts A, B and Follow-up) by Randomised Treatment	Change relative to average of screening triplicates	SAC[1]
3.49.	Safety	EG10	Summary of Maximum QTc Values Post-Baseline Relative to Period Baseline by Category (Parts A, B and Follow-up) by Period Treatment	IDSL	IA SAC [1], SAC [1]
3.50.	Safety	EG2	Summary of Change from Baseline in ECG Values (Parts A, B and Follow-up) by Randomised Treatment	IDSL	IA SAC [1], SAC [1]
3.51.	Safety	EG2	Summary of Change from Screening in ECG Values (Parts A, B and Follow-up) by Randomised Treatment	Change relative to average of screening triplicates	SAC [1]
3.52.	Safety	EG2	Summary of Change from Period Baseline in ECG Values (Parts A, B and Follow-up) by Period Treatment	IDSL	IA SAC [1], SAC [1]
3.53.	Safety	EG11	Summary of Maximum Increase in QTc Values Post-Baseline Relative to Baseline by Category (Parts A, B and Follow-up) by Randomised Treatment	IDSL	IA SAC [1], SAC [1]

Safety: Tables					
No.	Population	IDSL / Example Shell	Title	Programming Notes	Deliverable [Priority]
3.54.	Safety	EG11	Summary of Maximum Increase in QTc Values Post-Baseline Relative to Screening by Category (Parts A, B and Follow-up) by Randomised Treatment	Change relative to average of screening triplicates	SAC [1]
3.55.	Safety	EG11	Summary of Maximum Increase in QTc Values Post-Baseline Relative to Period Baseline by Category (Parts A, B and Follow-up) by Period Treatment	IDSL	IA SAC [1], SAC [1]
Vital Signs					
3.56.	Safety	VS1	Summary of Change from Baseline in Vital Signs (Parts A, B and Follow-up) by Randomised Treatment	ICH E3	IA SAC [1], SAC [1]
3.57.	Safety	VS1	Summary of Change from Period Baseline in Vital Signs (Parts A, B and Follow-up) by Period Treatment	ICH E3	IA SAC [1], SAC [1]
3.58.	Safety	VS7	Summary of Worst Case Vital Signs Results by PCI Criteria Post-Baseline Relative to Baseline (Parts A, B and Follow-up) by Randomised Treatment	IDSL	IA SAC [1], SAC [1]
3.59.	Safety	VS7	Summary of Worst Case Vital Signs Results by PCI Criteria Post-Baseline Relative to Period Baseline (Parts A, B and Follow-up) by Period Treatment	IDSL	IA SAC [1], SAC [1]

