Study Duration and Dosing	
 Each participant will participate in the study for approximately 20 weeks. This includes a screening period up to 30 days, an 84-day (12 week) treatment period, and a 28-day follow-up period after the last dose. Within 30 days of the screening visit (defined as day of consent signing), eligible participants enter a 2-part treatment phase as follows with study treatment starting on study day 1: 
 Part A: Approximately 36 participants are randomly assigned to receive either GSK2982772 60 mg three times daily (TID) or placebo TID for 42 days (6 weeks) in a 2:1 ratio. Part B: All participants who complete Part A move on to receive open label treatment of GSK2982772 60 mg TID for an additional 42 days (6 weeks). Treatment duration is a total of 84 days (12 weeks) inclusive of Parts A and B. Participants are followed-up for 28 days (4 weeks) after the last dose in Part B. Prior to amendment 01 being effective in each country, participants were randomly assigned to receive either: 
 Part A: GSK2982772 60 mg two times daily (BID) or placebo BID for 42 days (6 weeks) in a 2:1 ratio. Part B: Open label treatment for all participants who have completed Part A of GSK2982772 60 mg BID for an additional 42 days (6 weeks). 																															
Time & Events	
 Refer to Appendix 2: Schedule of Activities. During the 84-day (12 week) treatment period, participants attend the clinical for visits on Days 1, 15, 29, 43, 57, 71 and 85. At specific visits, participants must not take treatment prior to their scheduled treatment. On Days 8, 22, 36, 50, 64 and 78 participants were to be contacted by telephone and asked about their general health. Participants are given a diary card at every visit and asked to record daily study 																															

Overview of Study Design and Key Features	
	medication, concomitant medication and adverse events.

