Treatment Assignment	
 • At Screening a unique CRF number (Subject Number) is assigned. • Participants who meet screening eligibility criteria and complete pre-treatment assessments are randomised through an Interactive Response Technology System (IRTS). The IRTS confirms the participant's CRF number (Subject Number) and provides the randomisation number. • The randomisation number is generated by Clinical Statistics, prior to the start of the study, using validated internal software. Once assigned, this randomisation number must not be reassigned to any other participant in the study. • The randomisation is centrally controlled by the IRTS. • Approximately 36 participants were randomised in a 2:1 ratio to receive GSK2982772 60mg TID or Placebo TID in Part A. • Any participant that is re-screened outside of the allowed screening window at the approval of the GSK Medical Monitor, must be assigned a new unique Subject Number.

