5. CONSIDERATIONS FOR DATA ANALYSES AND DATA HANDLING CONVENTIONS

5.1. Study Treatment & Sub-group Display Descriptors

One subject was randomised to a BID regimen before the protocol was amended. Per instructions in the protocol, data will be summarised in tables and figures by treatment (GSK2982772 60mg or Placebo) irrespective of dosing regimen received (BID or TID). Data will be listed per treatment and dosing regimen received (BID or TID). Some key safety endpoints will be summarised by both randomised treatment and period treatment, details are provided in [Appendix 9](#).

Should a participant receive the wrong medication at any point during the study in error, that participant will be treated as having received GSK2982772 60mg TID for the duration of the study.

Randomised Treatment Group Descriptions					
RandAll NG		Data Displays for Reporting			
Code	Description	Description in tables/non-PK figures	Order in TF	Description in Listings/PK figures	Order in Listing
A	GSK2982772 60mg BID (Double-blind)	GSK2982772 60mg	2	GSK2982772 60mg BID	3
C	GSK2982772 60mg TID (Double-blind)	GSK2982772 60mg	2	GSK2982772 60mg TID	4
P	Placebo BID (Double-blind)	Placebo	1	Placebo BID	1
Q	Placebo TID (Double-blind)	Placebo	1	Placebo TID	2

Period Treatment Group Descriptions					
RandAll NG		Data Displays for Reporting			
Code	Description	Description in tables	Order in TF	Description in Listings	Order in Listing
A	GSK2982772 60mg BID (Double-blind)	GSK2982772 60mg	2	GSK2982772 60mg DB BID	3
B	GSK2982772 60mg BID (Open-label)	GSK2982772 60mg	2	GSK2982772 60mg OL BID	5
C	GSK2982772 60mg TID (Double-blind)	GSK2982772 60mg	2	GSK2982772 60mg DB TID	4
D	GSK2982772 60mg TID (Open-label)	GSK2982772 60mg	2	GSK2982772 60mg OL TID	6
P	Placebo BID (Double-blind)	Placebo	1	Placebo DB BID	1
Q	Placebo TID (Double-blind)	Placebo	1	Placebo DB TID	2

Treatment comparisons will be displayed as follows using the descriptors as specified:

- GSK2982772 60mg vs Placebo.

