7.1.1. Adverse Event Summary Measures

AE data will be summarised in tables and figures by the following:

- Part A by randomised treatment;
- Parts A, B and follow-up by randomised treatment;
- Parts A, B and follow-up by period treatment (i.e. treatment participant actually received).

AE data will be presented in data listings by the following:

- Parts A, B and follow-up by period treatment (i.e. treatment participant actually received).

Table 3 Overview of Planned Adverse Event Analyses

Endpoint / Parameter/ Display Type	Absolute		
	Summary		Individual
	T	F	L
Adverse Events (AEs)			
All AE by Maximum Intensity by SOC and PT	Y		
All Drug-Related AEs by Maximum Intensity by SOC and PT	Y		
Common ($\geq 10\%$) AEs / Drug-Related AEs by Overall Frequency	Y	Y ^[1]	
Common ($\geq 10\%$) Non-serious AEs by SOC and PT (Number of Subjects and Occurrences)	Y		
All AEs	Y		Y
Subject Numbers for Individual AEs			Y
Relationship Between AE SOCs, PT & Verbatim Text			Y
Serious and Other Significant AEs			
Serious AEs by SOC and PT (Number of Subjects and Occurrences)	Y		
Fatal Serious AEs			Y
Non-Fatal Serious AEs			Y
AEs Leading to Permanent Discontinuation of Study Treatment or Withdrawal from Study	Y		Y
Reasons for Considering as a Serious AE			Y
Possible Suicidality-Related AE (PSRAE)			Y

NOTES:

- T = Table, F = Figures, L = Listings, Y = Yes display generated, SOC = System Organ Class, PT = Preferred Term.
 - Summary = Represents TF related to any summaries (i.e. descriptive statistics) of the observed raw data.
 - Individual = Represents L related to any displays of individual participant observed raw data.
- 1: Plot of common AEs and relative risk will be generated.

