12.10.6. Safety Figures

Safety: Figures					
No.	Population	IDSL / Example Shell	Title	Programming Notes	Deliverable [Priority]
Adverse Events					
3.1.	Safety	AE10	Plot of Common ($\geq 10\%$) Adverse Events and Relative Risk (Part A only) by Randomised Treatment	IDSL	IA SAC [1], SAC [1]
3.2.	Safety	AE10	Plot of Common ($\geq 10\%$) Adverse Events and Relative Risk (Parts A, B and Follow-up) by Randomised Treatment	IDSL	IA SAC [1], SAC [1]
3.3.	Safety	AE10	Plot of Common ($\geq 10\%$) Adverse Events and Relative Risk (Parts A, B and Follow-up) by Period Treatment	IDSL	IA SAC [1], SAC [1]
Laboratory					
3.4.	Safety	LIVER14	Scatter Plot of Maximum Versus Baseline for ALT (Parts A, B and Follow-up) by Randomised Treatment	IDSL	IA SAC [1], SAC [1]
3.5.	Safety	LIVER14	Scatter Plot of Maximum Versus Period Baseline for ALT (Parts A, B and Follow-up) by Period Treatment	IDSL	IA SAC [1], SAC [1]
3.6.	Safety	LIVER9	Scatter Plot of Maximum ALT Versus Maximum Total Bilirubin ALT (Parts A, B and Follow-up) by Randomised Treatment	IDSL	IA SAC [1], SAC [1]
3.7.	Safety	LIVER9	Scatter Plot of Maximum ALT Versus Maximum Total Bilirubin (Parts A, B and Follow-up) by Period Treatment	IDSL	IA SAC [1], SAC [1]

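### Table 3.9 shows common (≥10%) adverse events by treatment received but selects them by randomised group, so it can list events below 10% in both of its columns

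*SAP*

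**What the plan says.** The title of Table 3.9 in SAP section 12.10.5 covers common (≥10%) "Adverse Events by Overall Frequency (Parts A, B and Follow-up) by Period Treatment". Its programming note repeats the one on Tables 3.7 and 3.8: an event qualifies if it reaches 10% "within either randomised treatment group".

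Section 7.1.1 explains period treatment as the treatment the participant actually received. In section 5.1, double-blind and open-label drug share one label in tables, so a table by period treatment has two columns, Placebo and GSK2982772 60mg.

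The two groupings differ because of the design in section 2.3. "Approximately 36 participants were randomised in a 2:1 ratio to receive GSK2982772 60mg TID or Placebo TID in Part A", and then "All participants who complete Part A move on to receive open label treatment of GSK2982772 60 mg TID". A placebo-randomised participant who enters Part B therefore belongs to the randomised placebo group throughout, but contributes to both period columns.

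Three other displays show common events by period treatment: Tables 3.15 and 3.18, and Figure 3.3 ("Adverse Events and Relative Risk (Parts A, B and Follow-up) by Period Treatment"). Their entries do not say which groups the 10% applies to.

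**The concern.** The 10% in the title of Table 3.9 is tested on one pair of groups and the percentages are printed for another. A programmer who follows the note literally can produce rows labelled common whose two printed percentages are both below 10%. Because the randomised placebo group also accumulates events that occur on open-label drug, a row can be selected on placebo-randomised participants even though nobody had the event while on placebo.

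Safety and tolerability is the primary objective, and Table 3.9 is the common-event summary by treatment received. What is at stake is whether its rows match its label, and whether it selects rows in the same way as the other common-event displays by period treatment.

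**Working it through.** The plan gives no figure on this point to reproduce, so the check compares the two selection rules by exact counting.

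**Inputs**
- About 36 participants at 2:1 (section 2.3), taken as 36 × 2/3 = 24 on drug and 36 × 1/3 = 12 on placebo.
- *m*, the number of placebo participants entering Part B, is not given. *m* = 12 is full entry; 0 to 12 was examined.
- Period columns: placebo 12, drug 24 + *m*. Denominators are assumed to be those who received that period treatment.
- The selection frequency is assumed to cover Parts A, B and Follow-up, as in the table title.

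**Notation.** *a* = drug-randomised participants with the event. Among the placebo-randomised, *p1* had it on placebo only, *p2* on open-label drug only, and *p3* on both.

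**Rules**
- As written: *a*/24 ≥ 0.10 or (*p1* + *p2* + *p3*)/12 ≥ 0.10.
- By the columns shown: (*a* + *p2* + *p3*)/(24 + *m*) ≥ 0.10 or (*p1* + *p3*)/12 ≥ 0.10.

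**Smallest qualifying counts at full entry**
- Randomised drug: 3/24 = 12.5% (2/24 = 8.3%).
- Randomised placebo, and the period placebo column: 2/12 = 16.7% (1/12 = 8.3%).
- Period drug column: 4/36 = 11.1% (3/36 = 8.3%).

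**Listed although below 10% in both columns (*m* = 12).** This needs *a* + *p2* + *p3* ≤ 3 and *p1* + *p3* ≤ 1, together with *a* ≥ 3 or *p1* + *p2* + *p3* ≥ 2. Fourteen count patterns satisfy it, or 11 if nobody has the event in both parts. Examples:

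| Who has the event | Selected on | Placebo column | Drug column |
|---|---|---|---|
| 2 placebo-randomised, both on open-label drug only | 2/12 = 16.7% | 0/12 = 0% | 2/36 = 5.6% |
| 3 drug-randomised | 3/24 = 12.5% | 0/12 = 0% | 3/36 = 8.3% |
| 1 placebo-randomised on placebo, 1 on open-label drug | 2/12 = 16.7% | 1/12 = 8.3% | 1/36 = 2.8% |

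Thirteen of the 14 patterns show 8.3% in at least one column. Only the first row of the table is lower than that in both.

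**Omitted although at 10% or more.** If both randomised groups are below 10%, then *a* ≤ 2 and *p1* + *p2* + *p3* ≤ 1. The placebo column is then at most 1/12 = 8.3%, and the drug column at most 3/(24 + *m*).
- *m* = 12: 3/36 = 8.3%. *m* = 7: 3/31 = 9.7%. No omission from 7 to 12 entrants.
- *m* = 6: 3/30 = 10.0%. *m* = 1: 3/25 = 12.0%. Omission is possible from 1 to 6 entrants, and only when *a* = 2 and exactly one placebo entrant has the event on open-label drug (with or without also having it on placebo).
- *m* = 0: none, because no placebo participant contributes to the drug column.

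So at 24:12, omission needs at least 6 of the 12 placebo participants not to enter Part B. The margin moves with the treated total. At 21:11, 3/(21 + *m*) ≥ 0.10 when *m* ≤ 9, so two non-entrants suffice. At 22:11 or 21:12 it takes three, and at 37 or more in total, seven or more. With 10 or fewer placebo participants it cannot happen: one case already gives at least 1/10 = 10%, so the event is selected.

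**After the change (*m* = 12).** Selection becomes at least 2/12 on placebo or at least 4/36 on drug. The 14 patterns drop out and no event is added.

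**The case against.** The strongest defence is that one fixed selection rule keeps the rows of Tables 3.8 and 3.9 identical, which allows comparison line by line, and that the rule as written is the more inclusive one at full entry. That is a workable display choice, but the SAP does not state it, and the title of Table 3.9 would then need a footnote saying that rows were chosen by randomised group.

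It is also fair that no event is lost from reporting by treatment received. Table 3.6 gives all adverse events by period treatment with no frequency cut, and Listing 16 lists them individually. This stands, and it limits the practical harm.

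The silence of Tables 3.15 and 3.18 and Figure 3.3 is weaker evidence. Several common-event tables by randomised treatment carry no note either, and all follow standard shells that are not reproduced in the SAP. Those three displays need the rule stated, but they do not contradict themselves.

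Two stronger readings are tempting. A reader might infer that Table 3.9 hides events at 10% or more on drug, particularly at the interim, for which it is also a deliverable. The documents do not support this. Part A completers all move to Part B, no omission arises at the planned numbers with full entry, and the SAP gives no interim numbers, only that an appropriate number will have completed 12 weeks. At partly enrolled sizes from 12:6 to 20:10, no omission is possible at any level of Part B entry. A reader might also infer that the extra rows are typically far below 10%. Most would show 8.3% in one column.

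**Conclusion.** The mismatch is real: the note on Table 3.9 applies the 10% threshold to groups that the table does not display. With 24:12 and full entry to Part B, the table can list events below 10% in both columns, as low as 0/12 and 2/36 (5.6%) and more often with 8.3% in one column. Whether it does so depends on the data. No event at 10% or more is omitted at these numbers; that would need half or more of the placebo group not to enter Part B, or a somewhat smaller treated total with a few non-entrants.

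The conclusion rests on the 24:12 split, on denominators of participants who received each period treatment, and on frequencies counted over Parts A, B and Follow-up. It is a minor labelling and selection fault in one descriptive table, and no analysis result depends on it.

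**What to change.** Change the Table 3.9 note so that common means at least 10% within either *period* treatment group, with participants who received that period treatment as the denominator. State the same rule for Tables 3.15 and 3.18 and Figure 3.3, so that all common-event displays by period treatment select on the groups they show.

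The cost is a few programming notes and no new data. There is a small downside. At the planned numbers the change only removes rows: an event in 3/24 drug-randomised participants, for instance, drops out of Table 3.9 at 3/36. The row set may then differ from Table 3.8. All such events stay visible in Table 3.6. If identical rows in Tables 3.8 and 3.9 are preferred, the alternative is to keep the note and add a footnote to Table 3.9 saying that events were selected by frequency in the randomised groups.
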